## 8.2.6. Pregnancy Testing

Serum pregnancy tests will be performed at Screening Visit S1. Further urine pregnancy tests may be performed, as determined necessary by the investigator, or required by local regulation, to establish the absence of pregnancy at all the study visits as detailed in the Schedule of Activities.

#### 8.3. Adverse Events and Serious Adverse Events

Timely, accurate, and complete reporting and analysis of safety information from clinical studies are crucial for the protection of participants, investigators, and the Sponsor, and are mandated by regulatory agencies worldwide. The Sponsor has established Standard Operating Procedures in conformity with regulatory requirements worldwide to ensure appropriate reporting of safety information; all clinical studies conducted by the Sponsor or its affiliates will be conducted in accordance with those procedures.

Adverse events will be reported by the participant (or, when appropriate, by a caregiver, surrogate, or the participant's legally acceptable representative) for the duration of the study.

The usual pharmacodynamic actions and expected effects of adenosine administration during CFR assessment are not considered as AEs.

As guselkumab is classified as a combination product, malfunctions or deficiencies of the device constituent will be reported as PQC.

For further details on AEs and SAEs (Definitions and Classifications; Attribution Definitions; Severity Criteria; Special Reporting Situations; Procedures) as well as PQCs, refer to Appendix 13, Adverse Events: Definitions and Procedures for Recording, Evaluating, Follow-Up, and Reporting.

# 8.3.1. Time Period and Frequency for Collecting Adverse Event and Serious Adverse Event Information

#### **All Adverse Events**

All AEs and special reporting situations, whether serious or non-serious, will be reported from the time a signed and dated ICF is obtained until completion of the participant's last study-related procedure, which may include contact for follow-up of safety. Serious adverse events, including those spontaneously reported to the investigator within 12 weeks after the last dose of guselkumab, must be reported using the Serious Adverse Event Form. The Sponsor will evaluate any safety information that is spontaneously reported by an investigator beyond the time frame specified in the protocol.

#### **Serious Adverse Events**

All SAEs occurring during the study must be reported to the appropriate Sponsor contact person by study-site personnel within 24 hours of their knowledge of the event.

Information regarding SAEs will be transmitted to the Sponsor using the Serious Adverse Event Form and Safety Report Form of the CRF, which must be completed and reviewed by a physician from the study-site, and transmitted to the Sponsor within 24 hours. The initial and follow-up reports of a SAE should be transmitted electronically or by facsimile (fax) via a secure transmission system.

Any possible Hy's law case (AST or ALT  $\geq$ 3x ULN together with bilirubin  $\geq$ 2X ULN or INR >1.5) is considered an important medical event and must be reported to the sponsor in an expedited manner using the Serious Adverse Event form, even before all other possible causes of liver injury have been excluded. The INR criterion is not applicable to participants receiving anticoagulants.

## 8.3.2. Follow-up of Adverse Events and Serious Adverse Events

Adverse events, including pregnancy, will be followed by the investigator as specified in Appendix 13, Adverse Events: Definitions and Procedures for Recording, Evaluating, Follow-up, and Reporting.

## 8.3.3. Regulatory Reporting Requirements for Serious Adverse Events

The Sponsor assumes responsibility for appropriate reporting of AEs to the regulatory authorities. The Sponsor will also report to the investigator (and the head of the investigational institute where required) all suspected unexpected serious adverse reactions (SUSARs). The investigator (or Sponsor where required) must report SUSARs to the appropriate Independent Ethics Committee/Institutional Review Board (IEC/IRB) that approved the protocol unless otherwise required and documented by the IEC/IRB.

All AEs will be recorded in the CRF and will be reported to the Sponsor as described under All Adverse Events in Section 8.3.1, Time Period and Frequency for Collecting Adverse Event and Serious Adverse Event Information.

#### 8.3.4. Pregnancy

All initial reports of pregnancy in female participants or partners of male participants must be reported to the Sponsor by the study-site personnel within 24 hours of their knowledge of the event using the appropriate pregnancy notification form. Abnormal pregnancy outcomes (eg, spontaneous abortion, fetal death, stillbirth, congenital anomalies, ectopic pregnancy) are considered SAEs and must be reported using the Serious Adverse Event Form. Any participant who becomes pregnant during the study must discontinue further doses of guselkumab.

Follow-up information regarding the outcome of the pregnancy and any postnatal sequelae in the infant will be required.

# 8.3.5. Disease-Related Events and Disease-Related Outcomes not Qualifying as Adverse Events or Serious Adverse Events

All events that meet the definition of a serious adverse event will be reported as SAEs, regardless of whether they are protocol-specific assessments.

The cause of death of a participant in a study ≤24 hours of the last dose of guselkumab, regardless of causality or association with guselkumab, is considered a SAE.

## 8.3.6. Adverse Events of Special Interest

Any newly identified malignancy or case of active TB occurring after the participant's first guselkumab administration must be reported within 24 hours by the investigator according to the procedures in Section 8.3 and Section 8.3.1. Investigators are also advised that active TB is considered a reportable disease in most countries. These events are to be considered serious only if they meet the definition of a SAE.

#### 8.4. Treatment of Overdose

No clinical studies in humans have been conducted to assess a toxic threshold for guselkumab. The highest single SC dose of guselkumab investigated in humans was 300 mg. The maximum IV dose (10 mg/kg) in humans was 987 mg.

In the event of an overdose (any dose greater than that prescribed for the study), the investigator or treating physician should:

- Contact the Medical Monitor immediately.
- Closely monitor the participant for AE/SAE and appropriate symptomatic treatment instituted immediately.

Decisions regarding dose interruptions or modifications will be made by the investigator in consultation with the Medical Monitor based on the clinical evaluation of the participant.

#### 8.5. Pharmacokinetics

Pharmacokinetics will not be evaluated for this study.

#### 8.6. Pharmacodynamics

Pharmacodynamics will be assessed as described in the endpoints.

#### 8.7. Biomarkers

Biomarker sample collections will be conducted at the time-points presented in the Schedule of Activities to measure serum markers. Data collected from these samples will be used for exploratory research that will include the following objectives:

- To understand the molecular effects of guselkumab.
- To understand psoriasis.

- To understand why people may respond differently to guselkumab.
- To develop tests related to guselkumab or psoriasis.

Instructions for the collection and shipment of these samples can be found in the appropriate Laboratory Manual.

#### 8.8. Medical Resource Utilization and Health Economics

Health Economics/Medical Resource Utilization and Health Economics parameters are not evaluated in this study.

#### 9. STATISTICAL CONSIDERATIONS

Statistical analysis will be done by the Sponsor or under the authority of the Sponsor. A general description of the statistical methods to be used to analyze the efficacy and safety data is outlined below. Specific details will be provided in the Statistical Analysis Plan.

Descriptive statistics, such as mean, standard deviation (SD), median, inter quartile range, minimum, and maximum for continuous variables, and counts and percentages for discrete variables will be used to summarize most data. In addition, graphical data displays (eg, line plots) and participant listings may also be used to summarize/present the data.

In general, for continuous or ordinal efficacy endpoints, a Mixed-Effect Model Repeated Measures (MMRM) model will be used. Covariates such as BMI, smoking status, presence, or absence of PsA, age, gender, left ventricular mass index and hypertension diagnosis will be incorporated into these models. For binary efficacy endpoints, 95% confidence intervals for binomial proportions will be provided using exact methods, such as Clopper-Pearson or Chan-Zhang.

In general, all statistical tests will be performed at a 2-sided significance level of  $\alpha$  0.05.

## 9.1. Statistical Hypotheses

The primary hypothesis of this study is that guselkumab is effective in reducing surrogate markers of cardiovascular risk as assessed by the change from baseline in CFR at Week 32.

#### 9.2. Sample Size Determination

The sample size calculation is based on the assumption that participants will show an average increase of 20% in CFR at Week 32. To detect a CFR mean change of 0.3 from baseline with 80% power, and assuming a SD of 0.8 and a 5% dropout rate, 50 participants are expected to be enrolled in the study.

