#### NUMBER OF PARTICIPANTS

Following screening for inclusion into the study, approximately 50 participants will be enrolled to receive subcutaneous injections of guselkumab (100 mg). The number of dropouts in the study are expected to be low; however, additional participants will be entered to maintain the sample size and ensure that the protocol-specified number of participants complete the study.

Approximately 20 of the enrolled participants should be active nicotine users. All participants will be instructed to abstain from nicotine-containing and caffeinated products for at least 12 hours prior to the cardiology assessments.

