#### STATISTICAL METHODS

[figure not shown]
The sample size calculation is based on the assumption that participants will show an average improvement of 20% in CFR at Week 32. To detect a CFR mean change of 0.3 from baseline with 80% power, and assuming a standard deviation of 0.8 and a 5% dropout rate, 50 participants are expected to be enrolled in the study. Sample size may be increased if the dropout rate is higher than expected, in accordance with the sample size assumptions stated above.

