## 4. STUDY DESIGN

# 4.1. Overall Design

This is an interventional, single-arm, open-label, oligocentric study to evaluate the effect of guselkumab on cardiovascular risk surrogate markers in adult men and women diagnosed with moderate-to-severe plaque psoriasis (with or without PsA) for at least 6 months prior to study entry. Participants will be assessed for eligibility at 2 screening visits; at Screening Visit S1, dermatology, medical history, and laboratory parameters will be assessed. Participants fulfilling eligibility criteria at Screening Visit S1 will be referred to the cardiology department and will undergo cardiologic assessments (cfPWV, GLS and CFR [via transthoracic doppler echocardiography]) at Screening Visit S2, and again at Week 0. Only participants with CFR  $\geq$ 2 and  $\leq$ 3.5 at both these time-points will be enrolled in the study. The CFR measurement at Week 0 will be considered as the baseline value.

Approximately 50 participants are planned to be enrolled, and will receive guselkumab (100 mg) SC at Weeks 0, 4, 12, 20 and 28. Approximately 20 of the enrolled participants should be active nicotine users. The number of nicotine users for enrollment in the study is capped at 20. Once this number is reached, only non-users may be enrolled to fulfil the sample size. Enrollment of nicotine users versus non-users will be stratified on a site-by-site basis. All participants will be instructed to abstain from caffeinated and nicotine-containing products at least 12 hours prior to any scheduled cardiology assessments.

The first dose of the guselkumab will always be administered at the site and by a health care professional (HCP). Subsequent doses can be self-administered under the supervision of site-staff after the participant has been adequately trained in the procedure.

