2. STATISTICAL HYPOTHESES

The primary hypothesis of this study is that guselkumab (administered as 100 mg at Weeks 0, 4, 12, 20 and 28) is effective in reducing surrogate markers of cardiovascular risk as assessed by the change from baseline of CFR measurement at Week 32 (i.e., change from baseline of CFR measurement at Week 32 is positive).

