5. STATISTICAL ANALYSES

5.1. General Considerations

Descriptive statistics (eg, mean, median, standard deviation (SD), minimum, and maximum) will be used to summarize continuous variables. Counts and percentages will be used to summarize categorical variables. Graphic data displays may also be used to summarize the data. In addition, graphical data displays (eg, line plots) and participant listings may also be used to summarize the data.

The summarized data will be presented by Nicotine-user, non-Nicotine user and total group.

Baseline Value: For all endpoints the last non-missing measurement prior to or on the day of the first administration of the study treatment (guselkumab) will be the Baseline value in the study (i.e., at 'Week 0, Baseline' analysis visit, following assignment of the actual visits using visit windows, as indicated in Table 2).

Level of Significance: In general, all tests will be performed at a 2-sided significance level of 0.05, unless otherwise specified. All interval estimations will be reported using 2-sided 95%CI. Nominal p-values will be presented.

Change from Baseline:

For the continuous variables pertaining to the cardiology outcomes, skin related outcomes, or paper PRO outcomes the determination of change from baseline will be determined only when both, baseline and the measurement for the particular visit is available.

Change from Baseline at visit x = Measurement from the visit x - Baseline value of the parmeter

The number of patients with missing change from baseline values will be also presented in the statistical outputs.

For continuous or ordinal efficacy endpoints, a Mixed-effect Model for Repeated Measures (MMRM) will be used. Covariates such as Nicotine use, body mass index (BMI), presence, or absence of PsA, age, gender, and visit will be incorporated into these models.

For binary efficacy endpoints, 95% confidence interval [CI] for binomial proportions will be provided using exact methods, such as Clopper-Pearson or Chan-Zhang.

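### At the only significance level the documents state (two-sided 5%), and with 0.8 read as the SD of change, 50 enrolled gives about 71–74% power for a CFR change of 0.3, not 80%

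*Protocol*

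**What the plan says.** Protocol 9.2 gives a "mean change of 0.3 from baseline with 80% power, and assuming a SD of 0.8 and a 5% dropout rate, 50 participants" as the basis for enrolment. The synopsis (Statistical Methods) and SAP section 3 carry the same five figures. Protocol 4.1 gives the target as "Approximately 50 participants are planned to be enrolled".

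None of these places names the test, the alpha or its sidedness, or says whether 0.8 is the SD of the change or of a single CFR value. Protocol 9.2 attaches a literature reference to the calculation, but the text does not say what was taken from it.

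A significance level appears in two other places. Protocol section 9 says that, in general, "all statistical tests will be performed at a 2-sided significance level of" 0.05. SAP 5.1 says "In general, all tests will be performed at a 2-sided significance level of 0.05, unless otherwise specified", and it also plans two-sided 95% confidence intervals. Neither the sample-size text nor the primary analysis section specifies another level.

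On dropouts, the synopsis (Number of Participants) and Protocol 7.1 say that "additional participants will be entered to maintain the sample size and ensure that the protocol-specified number of participants complete the study".

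**The concern.** The five design figures do not fit together at the level at which the study was to be tested. A reader who judges the design, or borrows the calculation for another CFR study, would take the risk of missing a true change of 0.3 to be 20%. At two-sided 5%, with 0.8 as the SD of change, that risk is about 26% with 50 completers and about 29% with 47 evaluable. If a one-sided level was used, the power claim and the planned analysis rest on different levels, and neither document says so.

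**Working it through.** **Inputs.** Mean change 0.3, SD 0.8, power 80%, dropout 5% and 50 enrolled come from Protocol 9.2, the synopsis and SAP section 3. Alpha, two-sided 0.05, comes from Protocol section 9 and SAP 5.1. The study is single-arm (Protocol 4.1), so the comparison is a one-sample test of the mean change against 0. **Assumption:** 0.8 is the SD of the change.

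**Step 1: reproduce 50.** With a one-sided 5% level, the noncentral t calculation needs 46 evaluable, and 46/0.95 = 48.4, so 49 enrolled. The normal approximation needs 44, and 44/0.95 = 46.3, so 47 enrolled. The one-sided t-test comes close to 50.

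**Step 2: the same at two-sided 5%.**
- Normal: n = (1.960 + 0.842)² × (0.8/0.3)² = 55.8, so 56 evaluable; 56/0.95 = 58.9, so 59 enrolled.
- Noncentral t: 57 gives 79.5% and 58 gives 80.2%, so 58 evaluable; 58/0.95 = 61.05, so 62 enrolled.

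Neither gives 50.

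**Step 3: power delivered by 50 enrolled.** With 5% dropout, 50 × 0.95 = 47.5, so 47 evaluable. If every dropout is replaced, 50 complete. The noncentrality is (0.3/0.8)√n, which is 2.571 at n = 47 and 2.652 at n = 50.

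| Evaluable | Two-sided 5%, t | Two-sided 5%, normal | One-sided 5%, t |
|---|---|---|---|
| 47 | 71.1% | 72.9% | 81.3% |
| 50 | 73.9% | 75.5% | 83.4% |

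The t-test figures, 71% and 74%, are the ones to quote. The normal approximation runs one to two points higher and does not reach 80% either.

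**Step 4: the size of the gap in other terms (t-test).** The change detectable with 80% power at two-sided 5% is 0.334 with 47 evaluable and 0.323 with 50. For a change of 0.3, 80% power would need a two-sided alpha of about 9.1% (n = 47) or 7.7% (n = 50).

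**Step 5: if 0.8 is a single-visit SD instead.** Then the SD of change is 0.8 × √(2(1 − ρ)), where ρ is the correlation between baseline and Week 32 within a participant. Neither document gives ρ, so the values below are a range of assumptions (two-sided 5%, t-test, 80% power).

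| ρ | SD of change | Evaluable | Enrolled |
|---|---|---|---|
| 0.40 | 0.876 | 69 | 73 |
| 0.50 | 0.800 | 58 | 62 |
| 0.55 | 0.759 | 53 | 56 |
| 0.60 | 0.716 | 47 | 50 |
| 0.65 | 0.669 | 42 | 45 |

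A correlation near 0.6 reproduces 50 exactly. The required enrolment moves by 28 participants across this range (73 − 45), so the correlation would have to be reported for the claim to be checked.

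**The case against.** Several points on the other side have force.

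*The number may have been calculated correctly.* A reader might infer from the shortfall that the sponsor made an arithmetic error. The documents do not support that. A one-sided 5% t-test gives 49 enrolled, which fits an approximate target of 50. It also fits the directional hypothesis in SAP section 2, that the "change from baseline of CFR measurement at Week 32 is positive". The two-sided rule is worded as a general default for analyses and is not tied to the sample-size paragraph. What this explains is where 50 came from. It does not give 80% power for the two-sided test that is planned, and SAP section 2 attaches no one-sided level to its hypothesis.

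*The SD may be of another kind.* The cited reference may show that 0.8 is a single-visit SD, and it was not available for this review. With a correlation near 0.6 the 80% claim would stand at two-sided 5%. This is the one reading of the SD that rescues the figure, and it needs an input that the text does not give.

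*The planned analysis is not a t-test.* It is an MMRM with covariates (Protocol section 9, SAP 5.3.3). A reader might infer that this planned analysis falls short of 80%. That cannot be shown: its power cannot be computed from the stated inputs. Adjustment would have to lower the SD of change from 0.80 to about 0.72 (n = 47) or 0.74 (n = 50). That means explaining about 1 − (0.719/0.8)² = 19% or 1 − (0.742/0.8)² = 14% of its variance, ignoring lost degrees of freedom. Neither document claims such a gain.

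*The expected effect is larger than 0.3.* Protocol 9.2 assumes that "participants will show an average increase of 20% in CFR at Week 32". At eligible baselines of 2 to 3.5 that is 0.40 to 0.70, and power for 0.40 is about 92% with 47 evaluable. A reader might infer that 0.3 was chosen as a cautious target, or that the two figures conflict. The text supports neither reading, because it never links them.

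*The calculation has been set aside.* SAP section 3 says it ceased to be relevant once the study was terminated, and SAP 5.1 labels the p-values nominal. This stands in full and limits the weight of the point.

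**Conclusion.** The stated 80% does not hold at the documented level on the natural reading of the SD. With a change of 0.3, an SD of change of 0.8 and a two-sided 5% one-sample t-test, power is about 71% with 47 evaluable and about 74% with 50 completers. The shortfall is 6 to 9 percentage points, and 80% would have needed about 12 more enrolled (62 against 50). Participants excluded for the intercurrent event in SAP 5.3.2 would lower the evaluable number further.

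The conclusion rests on 0.8 being the SD of change. It is a mismatch between the power claim and the stated alpha, or else an input left unreported. Severity is minor: this corrects a stated property of the design and changes nothing in the analysis that remains.

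**What to change.** Restate the power wherever the calculation is reported (Protocol 9.2, the synopsis and SAP section 3), according to what was actually done:

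- If 0.8 is the SD of change: *By one-sample t-test at two-sided 5%, power to detect a mean change of 0.3 (SD of change 0.8) is about 71% with 47 evaluable participants and about 74% with 50 completers; the change detectable with 80% power is about 0.33 with 47 evaluable.*
- If the calculation used a one-sided 5% level, say so and still give the two-sided power above, because the planned tests are two-sided.
- Keep 80% at two-sided 5% only if 0.8 was a single-visit SD, and then state the correlation used (about 0.6 would be needed).

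The text should not add a rationale for choosing 0.3 that the sponsor has not given.

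The cost is wording only, with no patients, data or analyses added. Under the first two options the stated power becomes less favourable. Protocol Appendix 12 requires a formal amendment to change the protocol, so with the study terminated, correcting SAP section 3 and carrying the corrected figure into the study report would be the lighter route.

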## 9.3. Populations for Analyses

For purposes of analysis, the following populations are defined:

Population	Description
Screened	All participants who sign the ICF
Full Analysis Set	All enrolled participants who receive at least 1 dose of guselkumab.
Safety	All enrolled participants who receive at least 1 dose of guselkumab.
Analysis Set	

## 9.4. Statistical Analyses

This section of the protocol is a summary of the planned statistical analyses of the most important endpoints including primary and key secondary endpoints. The Statistical Analysis Plan will be finalized within 3 months of "first patient in" (FPI). It will include a more technical and detailed description of the planned statistical analyses.

